8.2.5. Visit 5 (Week 6/Days 43)

This visit must occur 6 weeks/42 days (± 4 days) after Visit 2.

At this visit, the investigator or designee will perform the following procedures:

1. Query the subject/caregiver in a non-directive manner about any changes in the subject's health since the previous visit and report all AEs on the appropriate form
2. Query the subject/caregiver about any changes in the subject's concomitant therapies since the previous visit and report changes on the appropriate form
3. Confirm the subject continues to comply with all study restrictions, is eligible to continue in the study and has followed all study instructions
4. Measure vital signs
5. Identify any new lesions that require treatment (Treatment Area)
6. Determine BSA of EBS lesions in the Assessment Area and in the Treatment Area (if new lesions exist) using the palmar method; Note: the area being treated may not exceed 30% BSA
7. Perform the IGA evaluation on the Assessment Area
8. Dispense, collect and weigh study medication as appropriate
9. Dispense a blister lancing kit and instructions to the subject/caregiver if needed
10. Review the study instructions, including eDiary, use of body charts and approved bland, non-medicated, emollient/ moisturizer use, with the subject/caregiver
11. Schedule Visit 6 for Week 8/Day 57.

The investigator will mark the general location of all the EBS lesions on the appropriate body chart(s) at each study visit.

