8.2.7. Visit 7 (Week 12/Day 85)

This visit must occur 12 weeks/84 days (± 4 days) after Visit 2.

At this visit, the investigator or designee will perform the following procedures:

1. Query the subject/caregiver in a non-directive manner about any changes in the subject's health since the previous visit and report all AEs on the appropriate form
2. Query the subject/caregiver about any changes in the subject's concomitant therapies since the previous visit and report changes on the appropriate form

3. Confirm the subject continues to comply with all study restrictions, is eligible to continue in the study and has followed all study instructions
4. Measure vital signs
5. Perform a urine pregnancy test for WOCBP
6. Identify any new lesions that appeared since last visit
7. Determine BSA of EBS lesions in the Assessment Area and new lesions (if new lesions exist) using the palmar method
8. Calculate the total BSA of all EBS lesions
9. Perform the IGA evaluation on the Assessment Area
10. Dispense a blister lancing kit and instructions to the subject/caregiver if needed
11. Review the study instructions, including eDiary, use of body charts and approved bland, non-medicated, emollient/moisturizer use, with the subject/caregiver
12. Schedule Visit 8 for Week 16/Day 113.

The investigator will mark the general location of all the EBS lesions on the appropriate body chart(s) at each study visit.

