9.1.1. Investigator's Global Assessment (IGA)

The IGA is the investigator's (who must be a physician or Physician's Assistant/nurse practitioner in dermatology) clinical assessment of the average overall severity of all the EBS lesions, considered together, at a particular time point. The investigator should NOT refer to any other assessments, study photographs or notes to assist with these assessments.

At Visits 1-8, the investigator will assess the subject's EBS lesions using the scale below and report the one integer that best describes the average overall severity of all the EBS lesions considered together.

Investigator's Global Assessment	
Score	Definition
0	Clear: No blisters, no erosions, no crusting, no erythema and/or pigmentary changes may be present
1	Near Clear: Two or few small blisters, faint signs of erosion may be present, barely perceptible evidence of crusting, slight erythema
2	Mild: Predominantly small and some medium blisters, minimal erosions, clear crusting, definite well-defined erythema
3	Moderate: Mix of small and medium blisters, definite erosions, limited areas of crusting, marked erythema
4	Severe: Mix of medium and large blisters, marked erosions, ulceration may be present, marked and extensive crusting, intense erythema

For this evaluation, a blister is defined as a fluid filled thin-walled structure.

Blister size is defined as:

- Small: visible to $\leq 1\text{cm}^2$
- Medium: $>1\text{cm}^2$ to $\leq 2\text{cm}^2$
- Large: $>2\text{cm}^2$.

At Visit 1 (Week -6) for a subject to be enrolled, and at Visit 2 (Week 0) for the subject to be randomized, the IGA must be ≥ 3 .

At Visit 2 (Week 0) the investigator must complete the IGA prior to the first study medication application.

The IGA must be completed prior to the evaluator reviewing any study photographs.

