5.5. Non-Date Values

Every effort will be made to obtain required data at each scheduled evaluation from all subjects who have been enrolled.

For the primary analysis of the primary efficacy endpoint (proportion of subjects who achieve $\geq 60\%$ reduction in BSA of EBS lesions with the Assessment Area from Baseline to Visit 6/Week 8), subjects whose status at Week 8 is unknown will be defined to be a non-success/non-responder.

For sensitivity analysis of this endpoint, the following analyses will be performed:

1. Subjects with missing values at Week 8 in the Diacerein treatment group will be imputed as a success, while all subjects in the Placebo treatment group will imputed as a non-success.
2. Subjects with missing values at Week 8 in the Diacerein treatment group will be imputed as a non-success, while all subjects in the Placebo treatment group will imputed as a success.
3. Subjects with missing values at Week 8 will be imputed using multiple imputation (MI) under the assumption of missing at random (MAR). Based on the imputed value at Week 8, the subjects will be assigned accordingly as either a success or non-success.

Missing values for the BSA of EBS lesions within the Assessment Area will be imputed using multiple imputation methodology in two steps. Initially, ten datasets will be generated containing imputed values for non-monotone missing values in the original dataset. The variables used to guide this imputation will include the following: treatment group, age group (<8 and ≥ 8 years old), genotype (KRT5/KRT14 and Other), and BSA

of EBS lesions in the Assessment Area at Baseline, Week 1, Week 4, Week 8, and Week 16. In this step it will be assumed that any intermediate missing data points are MAR. In the second step, the remaining monotone missing values will be imputed. The same variables will be used to guide the imputation as in the first step.

For each imputation dataset, the proportion of subjects who achieve success will be analyzed using the Cochran-Mantel-Haenszel test described in Section 7.1 below. A log transformation will be performed to normalize the relative risk estimates and the standard error of the transformed estimate will be obtained from the log-transformed confidence limits for the relative risk estimate. The results from these ten analyses will be combined and then back-transformed to the original log scale. The corresponding relative risk estimate and confidence interval will be presented.

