For the key secondary endpoint, the same imputation methods will be employed as with the primary endpoint. No imputation will be performed on the other secondary or exploratory endpoints.

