7.1. Primary Efficacy Analysis

Descriptive summaries of the proportion of subjects who achieve $\geq 60\%$ reduction in BSA of EBS lesions will be presented by treatment group at each visit.

The primary endpoint is the proportion of subjects who achieve $\geq 60\%$ reduction in BSA of EBS lesions from Baseline to Visit 6 (Week 8). Subjects whose status at Visit 6 is unknown will be defined to be nonresponders. The primary analysis will be conducted using the Cochran-Mantel-Haenszel (CMH) test, stratified by genotype (KRT5/KRT15 and Other) and age group (<8 and ≥ 8 years old). Estimated relative risk, associated 95% confidence interval (CI), and p-values will be provided.

At the final analysis, the treatment groups will be compared using a two-sided test at the $\alpha=0.049$ level of significance in order to account for the alpha spent in the Interim Analysis as described in Section 10 below.

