7.2. Key Secondary Efficacy Analysis

The key secondary endpoint is the proportion of subjects achieving success on the IGA of the Assessment Area, where success on the IGA is defined as at least a 2-point reduction from Baseline to Visit 6 (Week 8). Subjects whose status at Visit 6 is unknown will be defined as non-responders. The key secondary endpoint will be analyzed using the CMH test, as described for the primary analysis. However, if the primary analysis is not statistically significant, then the results for the key secondary endpoint will be exploratory rather than confirmatory. This fixed sequence testing procedure maintains the overall level of significance for the primary and key secondary endpoints.

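### The multiple-imputation sensitivity analysis for Week 8 BSA success leaves out the Week 6 and Week 12 BSA values that the protocol collects

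*SAP*

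**What the plan says.** **Week 8 rule.** For the primary endpoint, SAP 5.5 states that "subjects whose status at Week 8 is unknown will be defined to be a non-success/non-responder". SAP 7.1 repeats this ("Subjects whose status at Visit 6 is unknown will be defined to be nonresponders"), and SAP 7.2 restates it for Week 8 IGA success ("Subjects whose status at Visit 6 is unknown will be defined as non-responders").

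**Sensitivity analyses.** SAP 5.5 adds three: two opposite extreme-case analyses and MI under missing at random. The MI runs in two steps, first for non-monotone gaps and then for the remaining monotone ones, with the same variables in both. They are treatment, age group, genotype, and BSA "of EBS lesions in the Assessment Area at Baseline, Week 1, Week 4, Week 8, and Week 16". The key secondary endpoint is to use the same imputation methods, but no IGA variable is named.

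**What is collected.** At Visit 5 (Week 6) protocol 8.2.5 requires the investigator to "Determine BSA of EBS lesions in the Assessment Area and in the Treatment Area (if new lesions exist) using the palmar method". At Visit 7 (Week 12) protocol 8.2.7 requires "Determine BSA of EBS lesions in the Assessment Area and new lesions (if new lesions exist) using the palmar method". For the IGA, protocol 9.1.1 says "At Visits 1-8, the investigator will assess the subject's EBS lesions using the scale below".

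**Week 16.** BSA and IGA success at Visit 8 are other secondary endpoints (SAP 3.1.3). SAP 5.5 says of that class: "No imputation will be performed on the other secondary or exploratory endpoints". SAP 7.3.2 and 7.3.3 analyse them by the CMH test used for the primary endpoint. SAP 4.1 places all efficacy analyses on the ITT population.

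**The concern.** The MI analysis is the only planned check on the primary result that models the missing values instead of setting them to an extreme. Its missing-at-random assumption is only as good as the variables it conditions on. Two kinds of subject are affected.

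- A subject who attends Week 6 and then leaves before Week 8 is imputed from Baseline, Week 1 and Week 4. The latest value, taken two weeks before the endpoint, is not used.
- A subject who misses only Visit 6 and returns has the nearest value on each side (Weeks 6 and 12) left out. Weeks 4 and 16 stand in.

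If leaving depends on how the lesions looked at Week 6, the data are missing at random given Week 6 but not given the listed variables alone. The stake is the reliability of a supporting analysis, not the primary test.

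There is also a smaller gap in wording. The rule for unknown status names Visit 6 or Week 8 each time it appears, while the Week 16 sections refer back to the primary method without saying how an unknown Visit 8 status is counted.

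**Working it through.** The plan gives no figure on this point. Its 77% power (SAP 11) reproduces as 77.7% for 40 per arm, 60% v 30%, two-sided 0.049, and is not affected.

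**1. Visits compared.** BSA is measured on study at Baseline and Weeks 1, 4, 6, 8, 12 and 16. The MI model has Baseline and Weeks 1, 4, 8 and 16. Weeks 6 and 12 are absent.

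**2. Information lost, subject last seen at Week 6.** The documents give no correlations, so both structures below are assumptions.

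- *Correlation decaying with time*, rho^(gap in weeks / 2). The latest earlier visit then carries all the information, so R² is that correlation squared.
  - Listed visits (latest is Week 4, gap 4 weeks): rho^4 = 0.24, 0.41, 0.66 for rho = 0.7, 0.8, 0.9.
  - With Week 6 (gap 2 weeks): rho^2 = 0.49, 0.64, 0.81.
- *Constant correlation r = 0.7*. With k earlier visits, R² = k r² / (1 + (k - 1) r).
  - Listed, k = 3: 1.47 / 2.40 = 0.61.
  - With Week 6, k = 4: 1.96 / 3.10 = 0.63.

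**3. Information lost, subject who misses only Visit 6.** Under decay only the nearest visit on each side matters. If these have correlations a and b with Week 8 and c with each other, R² = (a² + b² - 2abc) / (1 - c²). At rho = 0.7:

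- Weeks 4 and 16: a = 0.49, b = 0.2401, c = 0.1176, so R² = 0.2701 / 0.9862 = 0.27.
- Weeks 6 and 12: a = 0.70, b = 0.49, c = 0.343, so R² = 0.4948 / 0.8824 = 0.56.

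Under constant 0.7 the formula in step 2 gives 0.63 (k = 4) and 2.94 / 4.50 = 0.65 (k = 6).

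**4. Bias in the Week 8 relative risk.** Simulation with no drug effect and 600,000 subjects per arm. Success is the lowest 30% of change from baseline. The chance of being missing is logistic in the standardised Week 6 change (slope 1 or 2), worse lesions being missing more often. Imputation is by regression with residual noise. The true relative risk is 1.00. Missing rates are active v control.

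| Structure | Missing | MI as listed | MI with Week 6 |
|---|---|---|---|
| Decaying, rho 0.7-0.9 | 20% v 5% | 1.03-1.05 | 1.00 |
| Decaying, rho 0.7-0.9 | 10% v 5% | about 1.01 | 1.00 |
| Constant 0.7 | 20% v 5% | 1.02-1.03 | 1.00 |
| Constant 0.7 | 10% v 5% | about 1.01 | 1.00 |

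The bias favours the arm that loses more subjects, so it reverses if the rates are exchanged.

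**5. Week 16 denominator.** Take true success 30% in both arms, a fraction d missing, and missing subjects succeeding k times as often as observed ones. The observed-case rate is 0.30 / ((1 - d) + dk), and the non-responder rate is that times (1 - d). At 20% v 5% missing:

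- k = 0: observed-case 0.375 / 0.316 = 1.19; non-responder 0.30 / 0.30 = 1.00.
- k = 1: observed-case 0.30 / 0.30 = 1.00; non-responder 0.240 / 0.285 = 0.84.

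Each rule is unbiased where the other is not. At 10% v 5%, simulated false-positive rates (40 per arm, nominal 5%) are 4.8-5.2% under either rule.

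**The case against.** **The MI analysis is one of three sensitivity analyses, and the gain depends on an assumed structure.** Both points stand. If BSA has a stable subject level, earlier visits already carry most of what Week 6 would add (61% v 63%). The bias scenario also makes missingness depend on exactly the omitted visit, which is unfavourable to the listed model. The omission nevertheless has no stated reason, and the data are collected anyway.

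**Applying the same methods to IGA plainly means putting IGA in place of BSA.** That is the natural reading. The point is missing detail, not a contradiction.

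**A reader might infer that the Week 16 handling is an error, or that its denominator is evenly open.** The documents do not support this. Not imputing endpoints outside the fixed sequence is an explicit choice. Every non-responder statement names Week 8 or Visit 6, and SAP 7.2 restates the rule although it also refers back to the primary analysis. Observed-case is therefore the stronger reading. What supports the other reading is that SAP 5.5 defines unknowns as non-responders without calling this imputation, that SAP 7.3.2 and 7.3.3 refer back to the primary method, and that SAP 4.1 puts all efficacy analyses on ITT. That is enough to ask for a sentence.

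**A reader might also infer that non-responder scoring would be the better Week 16 rule, or that unequal Week 16 missingness would go unseen.** Step 5 shows that neither rule is uniformly less biased. SAP 6.1 tabulates withdrawals and their reasons, and SAP 7 and 7.1 plan summaries by visit and by-subject listings, from which either denominator can be rebuilt.

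**Evidence on dropout is mixed.** Protocol 8.8.8 withdraws subjects with moderate or severe diarrhea. But protocol 3.1 reports no treatment-related discontinuations in the earlier cream study, and protocol 7.7 keeps subjects who stop treatment on their visit schedule. Nothing in the documents establishes the 20% v 5% case.

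**Conclusion.** The MI model in SAP 5.5 omits two collected BSA values, one of them the last before the primary endpoint, and adding them is a better specification at almost no cost. The gain in explained Week 8 variance ranges from negligible (61% to 63%) to substantial (24% to 49%), depending on how BSA correlates over time. The bias is small: a relative risk of about 1.01 at 10% v 5% missing, and at most about 1.05 at 20% v 5%. Missing rates, correlations and the missingness mechanism are all assumptions, and the simulation is a large-sample limit without strata.

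This does not threaten the primary conclusion, whose main analysis does not use MI. Nor does it extend to Week 16, where the SAP plans no MI. The Week 16 point is a clarification only.

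**What to change.** 1. In SAP 5.5, list BSA at Baseline and Weeks 1, 4, 6, 8, 12 and 16 for both MI steps.
2. For the key secondary endpoint, name the model: treatment, age group, genotype and the IGA score from each of the same visits, and say how the imputed score becomes success or non-success.
3. In SAP 7.3.2 and 7.3.3, say whether unknown Visit 8 status is left out (observed-case) or counted as non-response, and report the other as a sensitivity analysis.

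SAP 1 allows revisions before database lock. The cost is wording, a little programming, and two more correlated predictors with about 80 subjects. If the fit proves unstable, Week 12 is the one to give up, since it cannot help a subject who leaves before Week 8. No new data are needed.

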6. ANALYSIS OF DISPOSITION AND SUBJECT CHARACTERISTICS

6.1. Disposition and Analysis Populations

Subject disposition information will be summarized. Counts (number and percent) of subjects who are randomized, who are treated with study medication, who complete the study, and who withdraw early from the study will be presented. The primary reasons for early withdrawals will also be tabulated. The Safety Population will be used as the denominator for the percentage calculations. Subject disposition, inclusion/exclusion criteria, and comments will be listed. The number and percent of patients in each analysis population will also be tabulated.

6.2. Protocol Deviations

A listing of all major protocol deviations will be provided.

6.3. Demographics and Baseline Characteristics

Demographic and baseline characteristics will be summarized by treatment for each of the analysis populations. Demographic and baseline characteristics include the following: age at informed consent, sex, race, ethnicity, genotype, IGA score at baseline, BSA of assessment area at baseline BSA of treatment area at baseline, total BSA of all EBS lesions at baseline, pruritus severity at baseline, pain severity at baseline, and mobility score at baseline. Unless otherwise stated, all continuous variables will be represented by n, mean, standard deviation, minimum, median, and maximum. All categorical variables will be presented as counts and percentages. Demographic characteristics will also be listed.

Baseline for all analysis variables will be the last measurement prior to the first application study medication, unless otherwise stated. For data collected from the eDiary, Baseline will be the value recorded from the first day that the subject received study medication.

Medical history will be summarized for the number and percentage of patients for each medical term. Medical history information will be listed. A listing of concomitant therapies/procedures will be provided.

6.4. Concomitant Medications

All medications administered during the study will be listed including the reported term, start and stop dates, and other relevant data will be provided. Concomitant medications include all medications taken on or after the date of the first treatment of study medication. Prior medications include all medications taken before the date of the first treatment of study medication and discontinued before the first treatment of study medication. All medications will be coded using the World Health Organization (WHO) Drug Sept 2016E B2 version.

7. ANALYSIS OF EFFICACY

Descriptive summaries of efficacy endpoints will be presented by treatment group and visit. All efficacy endpoints will be based on the Assessment Area, defined in the protocol, unless otherwise stated. The ITT population and PP population will be used for this analysis. A by-subject listing of efficacy endpoints will be provided.

7.1. Primary Efficacy Analysis

Descriptive summaries of the proportion of subjects who achieve $\geq 60\%$ reduction in BSA of EBS lesions will be presented by treatment group at each visit.

The primary endpoint is the proportion of subjects who achieve $\geq 60\%$ reduction in BSA of EBS lesions from Baseline to Visit 6 (Week 8). Subjects whose status at Visit 6 is unknown will be defined to be nonresponders. The primary analysis will be conducted using the Cochran-Mantel-Haenszel (CMH) test, stratified by genotype (KRT5/KRT15 and Other) and age group (<8 and ≥ 8 years old). Estimated relative risk, associated 95% confidence interval (CI), and p-values will be provided.

At the final analysis, the treatment groups will be compared using a two-sided test at the $\alpha=0.049$ level of significance in order to account for the alpha spent in the Interim Analysis as described in Section 10 below.

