8.2.2. Visit 2 (Week 0/Day 1)

This visit must occur within 42 days after Visit 1.

Subsequent study visit dates must be scheduled based on the date of Visit 2.

This visit may not occur until the investigator confirms all items necessary to determine a subject's eligibility for randomization are available.

At this visit, the investigator or designee will perform the following procedures PRIOR TO RANDOMIZATION:

1. Query the subject/caregiver about any changes in the subject's concomitant therapies since the previous visit and report changes on the appropriate form
2. Confirm the subject/caregiver continues to comply with all study restrictions and that the subject is eligible to continue in the study
3. Perform a urine pregnancy test for WOCBP; results must be negative for the subject to be randomized
4. Measure vital signs
5. Perform the IGA evaluation, IGA grade must be ≥ 3 in the Assessment Area
6. Confirm subject is eligible for randomization
7. Screen fail the study subjects who are not eligible for randomization. Note: subjects may be re-screened if, at a later date, the subject meets eligibility requirements. All protocol required procedures must be repeated (with the exception of genetic testing)
8. Perform Baseline ECG

For subjects who are eligible for randomization the investigator or designee will perform the following procedures:

1. Take standardized color photographs prior to the first study medication application
2. Determine Total BSA of the Assessment Area and of all EBS lesions using the palmar method
3. Identify the Reference Lesion and measure the Lesions Surface Area (LSA)
4. Collect blood & urine samples for clinical laboratory tests prior to the first study medication application
5. Register eligible subjects in the eDiary system in the IRT
6. Randomize eligible subjects
7. Weigh the study medication tube and dispense the tube to the subject
8. Instruct the subject/caregiver on the study medication application technique
9. Observe the first study medication application
10. Weigh the study medication tube after the first study medication application and then return the tube to the subject
11. Monitor the subject for at least 20 minutes after the application to detect any adverse events

12. Dispense a blister lancing kit and instructions to the subject/caregiver if needed
13. Review the study instructions, including eDiary, use of body charts and approved bland, non-medicated, emollient/moisturizer use, with the subject/caregiver

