8.3. EBS Lesion Identification

For this study, an EBS lesion is defined as a blister (*i.e.*, a fluid filled thin-walled structure), or the crust and/or erosion arising from a previous blister, and the immediately surrounding intense erythema. At Visit 1 (Week -6), for each subject the investigator will determine if the subject has EBS lesions that fulfill the inclusion criteria.

The EBS lesions must be on one or both of the following body areas:

- Localized involvement:
 - plantar or palmar areas only
 - plantar areas where >25% of the area has hyperkeratosis that has been present for greater than 12 weeks are excluded.
- Generalized involvement:
 - Arms from the shoulder to the tips of the fingers
 - Legs from the hip to the tips of the toes
 - Front and back of the torso, including the neck from the mandibular line in the front and the hairline in the back, to the beltline

The Assessment Area of EBS lesions to be treated must be $\geq 2\%$ and $\leq 30\%$ BSA at Visit 1 (Week -6) for the subject to be enrolled and at Visit 2 (Week 0) for the subject to be eligible for randomization. The area being treated must not exceed 30% BSA at any time.

Between Visit 1 (Week -6) and Visit 2 (Week 0) the status of EBS lesions may change, therefore, at Visit 2 (Week 0), the investigator will evaluate each subject to determine which of the following categories describe the subject's EBS lesions identified at Visit 1 (Week -6):

1. The V1 Assessment Area lesions do not meet the protocol requirements for the subject to be eligible for randomization, and the subject does not have EBS lesions that meet the requirements
2. The V1 Assessment Area lesions meet the protocol requirements for the subject to be eligible for randomization
3. The V1 Assessment Area lesions do not meet the protocol requirements for the subject to be eligible for randomization, but the subject has additional/other EBS lesions that meet the requirements. The Assessment Area is re-defined.

At Visit 2 (Week 0), the investigator will discharge subjects from the study who are in category 1.

At Visit 2 (Week 0), for subjects who are in category 2 or 3 the investigator will follow the procedures below to identify EBS lesions to be treated.

The investigator will mark the general location of all the EBS lesions on the appropriate body chart(s) at each study visit.

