2.2. Trial Design

This is an international, multicenter, randomized, double-blind, vehicle-controlled, parallel group study to evaluate the safety and efficacy of topical Diacerein 1% Ointment for the treatment of subjects with EBS. Subjects at least 4 years of age with a genetic confirmation of EBS (based on either existing documentation or results from a sample collected as part of the study) who meet all the inclusion criteria and none of the exclusion criteria at Visit 1 will be eligible for enrollment in the study.

Eligible subjects will be randomized in a 1:1 ratio to either receive 8 weeks of once-daily application of Diacerein 1% Ointment or Control Ointment to all EBS lesions. Approximately 80 subjects will be randomized at approximately 22 international investigational centers. The randomization will be stratified by genotype (KRT5 and/or KRT14 versus other genotypes) and age group (<8 and ≥8 years old). Subjects/caregivers will apply the assigned study medication to all EBS lesions, including any new EBS lesions that develop, once daily, every evening during the 8-week treatment period. No study medication applications will be made to any lesion that becomes infected until the infection resolves with appropriate investigational center specific medical care.

Subjects/caregivers will be instructed on the use of the electronic diary (eDiary) to record patient reported outcomes of pruritus, pain and mobility and to document bandage use, blister lancing compliance, new lesions that develop in between study visits, routine cleanser use and study medication applications. Adverse events, clinical laboratory data, pharmacokinetic (PK) sampling, efficacy evaluations and determination of study medication use will be routinely collected.

The duration of study participation is anticipated to be a maximum of 158 days per subject (~22 weeks). This includes the up to 6-week screening period, an 8-week treatment period and an 8-week no-treatment follow-up period.

Study visits are summarized as follows:

- Visit 1 (Week -6/Day -42 to 0) enrollment, start randomization eligibility assessment period
- Visit 2 (Week 0/Day 1) randomization; first study medication application
- Visit 3 (Week 1/Day 8) treatment period follow-up
- Visit 4 (Week 4/Day 29) treatment period follow-up
- Visit 5 (Week 6/Day 43) treatment period follow-up
- Visit 6 (Week 8/Day 57) end of the treatment period
- Visit 7 (Week 12/Day 85) no treatment follow-up

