3. STUDY ENDPOINTS

3.1. Efficacy Variables

3.1.1. Primary Endpoint

The proportion of subjects who achieve $\geq 60\%$ reduction in BSA of EBS lesions within the Assessment Area from Baseline to Visit 6 (Week 8).

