11. SAMPLE SIZE AND POWER CONSIDERATIONS

The original sample size calculation was based on the endpoint of the proportion of subjects with $\geq 40\%$ reduction in BSA of EBS lesions at Week 16. The assumed true rates were 60% and 30% in the Diacerein 1% Ointment and Control Ointment groups, respectively. Based on a two-sided, two-sample comparison of proportions at the $\alpha=0.049$ level of significance, a total sample size of 80 subjects provides 77% power. No data are available on which to base a sample size calculation for the primary endpoint, now defined at Week 8 and now based on the proportion of subjects with $\geq 60\%$ reduction in BSA.

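### The primary CMH test is valid but leaves out baseline Assessment Area BSA; adding it as a continuous covariate is a cheap improvement, worth from about -1 to about +6 points of power in most settings checked.

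*SAP*

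**What the plan says.** The primary endpoint (SAP 3.1.1) is a fall of at least 60% from baseline in the BSA of lesions within the Assessment Area at Week 8. On the test, SAP 7.1 says: "The primary analysis will be conducted using the Cochran-Mantel-Haenszel (CMH) test, stratified by genotype" and age group. These factors correspond to the allocation scheme in SAP 2.2: "The randomization will be stratified by genotype (KRT5 and/or KRT14 versus other genotypes) and age group". SAP 7.3.2 applies the same test at Week 16.

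Baseline BSA is available for every randomised subject. Protocol 8.2.2 requires the site at Visit 2 to "Determine Total BSA of the Assessment Area and of all EBS lesions using the palmar method", and lists this ahead of randomisation and the first application. Protocol 8.3 sets an entry range of 2% to 30% at Visits 1 and 2 and adds: "The area being treated must not exceed 30% BSA at any time". (Inclusion criterion 3 gives only the 2% floor.)

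The SAP uses this variable in two other places. Section 6.3 lists "BSA of assessment area at baseline" among the characteristics summarised by arm, and section 5.5 puts it in the multiple-imputation model. The imputed datasets are then analysed with the same CMH test, so no analysis of BSA success adjusts for baseline BSA. By contrast, the ANCOVA of percent change in Reference Lesion area (SAP 7.3.1) has the lesion's baseline area as a covariate.

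**The concern.** A percent-of-baseline outcome can still depend on baseline, because baseline is its denominator. If baseline BSA predicts success, a test that ignores it has less power than one that uses it, with the same patients. Randomisation is not stratified by BSA, so in a trial of this size the arms can differ on it by chance, and the planned test has no means of correcting for that.

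The stakes are highest at the interim. SAP 10 bases an efficacy boundary, a 10% conditional-power futility rule and a sample size re-estimation on 40 subjects, about 20 per arm. The last two use the observed treatment difference directly. The margin is also thin: SAP 11 says that "a total sample size of 80 subjects provides 77% power", against the 80% used in Protocol 11.4.

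**Working it through.** **Inputs.** 40 per arm, 60% against 30%, two-sided alpha 0.049 (SAP 7.1 and 11). SAP 11 says these rates belong to the superseded endpoint (at least 40% reduction at Week 16) and that no data exist for the current one. All power figures are therefore illustrative. The documents give no association between baseline BSA and success, so it is varied below.

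**1. The stated power.** Pooled two-proportion formula, with critical value 1.969 and mean rate 0.45:

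z = [0.3 × √40 − 1.969 × √(2 × 0.45 × 0.55)] / √(0.24 + 0.21) = (1.897 − 1.385) / 0.671 = 0.764, so power is 77.7%. The SAP's 77% is reproduced.

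**2. Could baseline be prognostic?** Let r be the correlation of log baseline with log Week 8 BSA, and k the ratio of their SDs (Week 8 over baseline). Then

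corr(log baseline, log ratio) = (rk − 1) / √(1 + k² − 2rk).

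At r = 0.5 this is −0.50 for k = 1, −0.33 for k = 1.25, −0.19 for k = 1.5 and 0 for k = 2. An association is plausible, but its size is open and it can vanish.

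**3. From the latent scale to the binary endpoint.** Dichotomising weakens a correlation by the factor φ(c)/√(p(1−p)), where c is the normal cut-point for success rate p. The factor is 0.789 at p = 0.6 and 0.759 at p = 0.3. A latent 0.5 thus becomes 0.39 and 0.38.

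**4. Change in power.** Two simulation models were used, with the genotype and age strata taken as non-prognostic and their sizes assumed.

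| Model | Association | Planned CMH | Adjusted | Change (points) |
|---|---|---|---|---|
| CMH on baseline-adjusted residuals | latent 0 | – | – | −0.8 |
| | latent 0.2 | 77.9% | 78.2% | +0.3 |
| | latent 0.4 | 77.8% | 80.9% | +3.1 |
| | latent 0.5 | 77.9% | 83.6% | +5.7 |
| Logistic score test, log BSA | OR 1 per SD | 79.8% | 79.8% | 0 |
| | OR 1.5 | 79.4% | 80.4% | +1.0 |
| | OR 2 | 78.7% | 82.8% | +4.1 |
| | OR 3 | 78.4% | 87.4% | +9.0 |

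With log BSA uniform over 2% to 30%, the range spans √12 = 3.46 SD, so OR 3 per SD means an odds ratio of about 45 from end to end. That is an extreme case.

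Adding a median split of BSA as a further CMH stratum gave 76.3%, 76.8%, 78.1% and 82.6% in the four logistic settings. That is below the planned test in the first three.

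**5. Chance imbalance.** The between-arm difference in standardised log BSA has SD √(2/n).

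| Per arm | SD of difference | P(above 0.3 SD) | P(above 0.5 SD) |
|---|---|---|---|
| 40 | 0.224 | 18% | 2.5% |
| 20 (interim) | 0.316 | 34% | 11% |

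A 0.224 SD imbalance moves the risk difference by about 0.2475 × ln(OR) × 0.224, which is 2, 4 or 6 percentage points at OR 1.5, 2 or 3 per SD.

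**6. Type I error.** Over all randomisations, the planned CMH rejected 4.7% to 5.6% of true nulls in the logistic simulations (nominal 4.9%, Monte Carlo error about 0.3 points). Given a particular imbalance it can be higher. At 40 per arm and latent correlation 0.4, the rate is about 5.8% at 0.3 SD and 9% to 10% at 0.5 SD.

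**The case against.** The planned test is valid, its factors correspond to the randomisation strata, and SAP 6.3 will make any imbalance visible. The endpoint is already relative to each subject's own baseline, so a 15-fold entry range (30/2) does not by itself make baseline prognostic. Counting unknown Week 8 status as non-response may dilute any association further. An adjusted statistic carried through the interim and the Cui-Hung-Wang final test adds complexity at about 20 per arm. All of this stands, and it limits the point to an improvement.

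A reader might infer several stronger things that the documents do not support:

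- **That power is being lost.** No section links baseline BSA to achieving the reduction. With no association the loss is zero.
- **That adjustment would gain 11 points (77.7% to 88.5%).** This follows only if 0.5 is taken as the correlation with the binary outcome. If 0.5 is the latent correlation, step 3 brings it down to 0.38–0.39. The same approximation then gives about 84%, in line with the simulated 83.6%.
- **That coarse palmar measurement makes small areas respond less.** Protocol 9.1.5 defines 1% BSA as the subject's hand but does not say that whole palms are recorded. Even if they are, the fall needed is not monotone: 100% at 2 palms, 67% at 3, 75% at 4, 60% at 5, 71% at 7 and 60% at 10.

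What the objection does not answer is the SAP's own practice. For the Reference Lesion, also analysed as percent change, the SAP adjusts for baseline; for the primary endpoint it does not, and it gives no reason.

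**Conclusion.** The omission is real, but it is a missed efficiency and not an error. Adjustment would change power by about −1 to 0 points at latent correlations of 0 to 0.2, by +3 to +4 at moderate association (latent 0.4, or OR 2 per SD), and by about +6 at latent 0.5. The +9 at OR 3 per SD is an upper case. These figures rest on 80 subjects, response rates set for a superseded endpoint, and an association that must be assumed.

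The second benefit is protection against chance imbalance, mainly at the interim, where a difference above 0.5 SD arises in 11% of trials; at 40 per arm it arises in only 2.5%. It would be wrong to conclude that the planned test has inflated type I error, since over all randomisations it stays near nominal. Imbalance matters conditionally, and only if baseline BSA is prognostic.

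**What to change.** In SAP 7.1 and 7.3.2, keep the genotype and age strata and add log baseline Assessment Area BSA as a continuous covariate. One way is a stratified randomisation-based ANCOVA (CMH on covariate-adjusted residuals) for the p-value, with a covariate-standardised relative risk and 95% CI so that the planned effect measure is kept. Do not add BSA as a further CMH stratum: that makes eight cells for 80 subjects and can lower power.

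Use the same adjusted statistic for the interim boundary, the conditional power, the re-estimation and the Cui-Hung-Wang final test. Keep the unadjusted CMH as a sensitivity analysis. If the sponsor prefers to leave the primary test as it is, the minimum is to pre-specify the adjusted analysis as supportive.

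The cost is SAP wording and a few lines of code, with no new data or patients. SAP 1 allows revision until database lock, but this change should be settled before any unblinded analysis. The downside is about 1 point of power (allow up to about 2) if baseline BSA proves not to be prognostic.
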